1.2.1 PRE-CLINICAL DEVELOPMENT OF TGR-1202

The potency of TGR-1202 against the human and mouse δ isoform of PI3K was evaluated in a homogeneous time resolved fluorescence (HTRF) based enzyme assay in the presence of ATP at its Km value (100 μ M) (11). Selectivity over the other three isoforms, namely, α , β , and γ was also determined (2011) (AKT phosphorylation in THP-1 cells. Study Report IVT-5264-APT-08, 2011) (AKT phosphorylation in MOLT-4 cells. June Study Report IVT-5264-APM-10, 2011).

Data demonstrated the specificity of TGR-1202 towards PI3K δ with >1000, 50 and 48-fold selectivity over α , β , and γ , respectively in an enzyme based assay, indicating that the primary mode of action of this compound is via inhibition of the δ isoform.

[figure not shown]

FIGURE 1: TGR-1202 POTENCY AGAINST HUMAN AND MOUSE PI3K ISOFORMS

[figure not shown]
PI3K isoforms (Human)	IC50 (nM)
α	>10,000
β	1,116
γ	1,065
δ	22.23

Proliferation of immortalized leukemic cells representative of various indications was determined by a MTT (3-(4,5-Dimethylthiazol-2-yl)-2,5-diphenyl tetrazolium bromide) assay (17). Cells were incubated with TGR-1202 for different time-periods (72 -96 h) based on their doubling time. Data demonstrated the ability of TGR-1202 to inhibit leukemic cell proliferation albeit with different potencies based on the cell type.

Overall, a 50% growth inhibition for majority of B, T, and monocytic cell lines was achieved at a concentration between 0.5 -7.5 μ M of TGR-1202.

Subsequent to cell viability, the effect of TGR-1202 on AKT phosphorylation (12, 13, 14, 15, 16) was determined. AKT, a serine threonine kinase mediates the downstream effects of PI3K activity and modulates several cell processes including survival and growth. Reduction of phosphorylated AKT by TGR-1202 in representative cell lines was determined by Western blotting using a phospho-AKT (Ser473) antibody.

[figure not shown]
FIGURE 2: REDUCTION OF PAKT BY TGR-1202 IN CELL LINES BY WESTERN BLOTTING

1.2.1.1.1 IN-VIVO ACTIVITY

In vivo efficacy of TGR-1202 was confirmed in a subcutaneous mouse MOLT-4 xenograft model. Oral administration of 150 mg/kg/QD over a 25-day period resulted in a significant delay in tumor growth.

FIGURE 3: TGR-1202 IN VIVO EFFICACY

1.2.1.1.2 TOXICOLOGY

To assess the safety and toxicity of TGR-1202 a 28-day repeat dose study with a 14-day recovery period was conducted in CD-1 mice and beagle dogs, to evaluate the potential reversibility of findings and to support the use in humans. TGR-1202 was administered orally in order to mimic the planned mode of clinical administration.

Once daily oral administration of TGR-1202 was tolerated in mice at free base dose levels of 50 and 150 mg/kg/day. Increases in liver weights, microscopic findings in the liver and the increases in serum cholesterol, and female only ALT, AST, and GGT levels were observed at 750 mg/kg/day of free base (the highest dose tested) and were considered adverse. The no-observed-adverse-effect level (NOAEL) was considered to be 150 mg/kg/day in mice.

Once daily oral administration by capsule of TGR-1202 was well tolerated in dogs at levels of 50 and 150 mg/kg/day. The gastrointestinal tract, based on clinical signs, was the target organ system. Based on effects on body weight and the incidence and severity of emesis and diarrhea, the NOAEL was considered to be 150 mg/kg/day (114.5 mg/kg/day as free base) in this species.

Refer to the Umbralisib Investigator's Brochure (IB) for detailed information on toxicology studies conducted to date.

TGR-1202-201-CLL

1.2.2 CLINICAL DEVELOPMENT OF UMBRALISIB

1.2.2.1 SINGLE-AGENT IN PATIENTS WITH RELAPSED OR REFRACTORY HEMATOLOGIC MALIGNANCIES

Umbralisib is under evaluation in an ongoing single-agent Phase I dose-escalation study in patients with relapsed and refractory hematologic malignancies (Burris et al, ASH 2014). Fifty-five patients were enrolled and eligible for safety evaluation, with 43 patients evaluable for efficacy. The median age was 62 years (range 22-82), 73% male and 18/55 enrolled patients had a diagnosis of CLL. Among all patients the median number of prior therapies was 3, with 80% receiving prior rituximab-based chemotherapy. Other histological diagnoses included; FL (n=15), HL (n=9), DLBCL (n=7), MCL (n=2), MZL (n=2), HCL and WM (n=1 each). The majority of patients had an ECOG of 1 and 51% received 3 or more prior therapies.

Patients have been enrolled in a 3+3 dose-escalation design starting at 50 mg QD with subsequent cohorts evaluating doses as high as 1800 mg QD. In an effort to further improve the oral bioavailability of umbralisib, the particle size of the drug product was reduced through a micronization process, resulting in greater absorption when tested in a bioequivalence crossover study in healthy subjects (see Section 1.2.2.2 Healthy Subject Pharmacokinetic Studies below). This micronized formulation was introduced into dose escalation at 200 mg QD and dosed as high as 1200 mg QD, with no maximum tolerated dose (MTD) reached. Intra-patient dose escalation rules have allowed patients enrolled into the study in early cohorts to increase their dose of umbralisib as subsequent higher cohorts have cleared safety evaluation.

A dose-dependent response has been observed with umbralisib, with a dose of 800 mg or higher of the initial formulation or any dose of the micronized formulation producing significant nodal reductions among CLL patients. Of the 14 evaluable CLL patients treated at or above this therapeutic threshold, 93% have achieved a nodal partial response, and nodal reductions show an improvement with time on umbralisib with a median time on study of 6 months. Adverse events observed amongst all 55 patients included diarrhea, nausea, fatigue, cough, anorexia, headache, vomiting, rash, neutropenia, constipation, dyspnea, and thrombocytopenia. One DLT event of Grade 3 rash was observed at the 800 mg dose level of the initial formulation, which necessitated enrollment of an additional 3 patients. The Grade 3 rash resolved upon suspension of umbralisib and concomitant medications and did not recur upon re-challenging the patient at 800 mg QD. See the umbralisib investigators brochure for a complete overview of the umbralisib side effect profile.

Dosing of umbralisib initially occurred in the fasting state, but was transitioned mid-study to fed state dosing, with patients instructed to take umbralisib with food. All dosing of umbralisib is now conducted using the micronized formulation and in the fed state.

Overall, umbralisib was well tolerated and displayed promising signs of clinical activity at the higher dosing cohorts with 800 mg QD selected as the Phase 2 dose in patients with CLL. Dose expansion in the Phase 1 study continues.

In parallel with the Phase 1 single-arm, dose-escalation study in patients with relapsed or refractory hematologic malignancies; two healthy subject, crossover, bioequivalence pharmacokinetics studies have been completed. The first pharmacokinetic study was a Phase 1 drug-food interaction study with a single 200 mg oral dose of TGR-1202 in healthy volunteers followed by a second single dose Phase 1 pharmacokinetic study evaluating the absorption, distribution, metabolism and excretion characteristics of two different oral formulations of 200 mg TGR-1202 (original formulation vs. micronized formulation) in healthy volunteers.

1.2.2.2.1 TGR-1202-PK101: FOOD EFFECT

Study TGR-1202-PK 101 was two-period, randomized, two-way crossover, drug-food, drug-gender interaction study in 24 healthy subjects (12 males and 12 females) to assess the mean plasma TGR-1202 concentration over time following a single oral dose of 200 mg of TGR-1202 under fasting and fed condition using the original formulation. In general, administration of TGR-1202 under fed conditions results in a higher rate of exposure relative to when the product was given under fasting conditions.

The statistical comparisons of TGR-1202 pharmacokinetic parameters under fasted and fed condition are shown below.

D	Geometric LS Means		% Geometric	Confidence Interval	
Parameters	Fasting	Fed	Mean Ratio	Confidence interval	
AUC _{0-t} (ng·hr/mL)	6029.87	962.02	160.73	140.25 - 184.21	
AUC _{0-inf} (ng·hr/mL)	8391.35	14047.17	167.40	141.59 - 197.92	
C _{max} (ng/mL)	176.78	483.15	273.31	234.04 - 319.17	

Food increased both the extent and rate of exposure of TGR-1202. The extent (AUC_{0-t}) and total extent (AUC_{0-inf}) of exposure increased by 61% and 67%, respectively, when TGR-1202 was administered under fed conditions compared to fasting conditions. The peak plasma levels of TGR-1202 increased by over 173% when TGR-1202 was administered with food.

Using these mean values, a 334 mg oral dose of TGR-1202 under fasted condition can be extrapolated to be equivalent to an oral dose of 200 mg of TGR-1202 under fed conditions in terms of exposure based on AUC_{0-inf} .

1.2.2.2.2 TGR-1202-PK102: FORMULATION EFFECT

Study TGR-1202-PK 102 was a two-period, randomized, two-way cross over, relative bioavailability and pharmacokinetic bioequivalence study with two different drug product formulations of TGR-1202. In this study, TGR-1202 was administered under fasted conditions in 24 healthy subjects (12 males and 12 females) to assess the mean plasma TGR-1202 concentration over time following a 200 mg single dose of the original drug product formulation and modified (micronized) drug product formulation of TGR-1202. The mean rate and extent of exposure to TGR-1202 were higher following administration of the micronized drug product formulation compared to the original drug product formulation as mean concentrations were higher throughout most of the sampling interval.

TGR-1202-201-CLL

[figure not shown]
The statistical comparison of the micronized 200 mg drug product formulation versus the original 200 mg drug product formulation are shown below:

	Geometric	LS Means	%	Confidence Interval	
Parameters	Original Formulation	Micronized Formulation	Geometric Mean Ratio		
AUC _{0-t} (ng·hr/mL)	5906.11	9439.82	159.83	149.43 - 170.95	
AUC _{0-inf} (ng·hr/mL)	7715.67	12378.19	160.43	146.49 – 175.70	
C _{max} (ng/mL)	166.20	371.70	223.65	202.33 - 247.20	

The micronized drug product formulation increased both the extent and rate of exposure of TGR-1202 under fasted conditions. The extent (AUC_{0-t}) and total extent (AUC_{0-inf}) of exposure both increased by 60%, respectively, following administration of the modified drug product formulation relative to original drug product formulation. The Peak plasma (C_{max}) levels of TGR-1202 increased by over 124% following administration of the micronized drug product formulation relative to original drug product formulation under fasted conditions.

Using these mean values, a 320 mg oral dose of TGR-1202 in the original formulation under fasted condition can be extrapolated to be equivalent to an oral dose of 200 mg of the original formulation TGR-1202 under fasted conditions in term of exposure based on AUC_{0-inf}.

The improved exposure seen with the micronized formulation of TGR-1202 was confirmed in patients in the Phase 1 dose escalation as well. The chart below illustrates the pre-dose plasma concentrations of TGR-1202 on Day 1 of Cycle 2 in patients administered equivalent doses of either the initial formulation in the fasting state or the micronized formulation in the fed state:

1.3 RATIONALE FOR THE PHASE 2 TRIAL

A retrospective analysis of 123 patients who discontinued prior kinase inhibitor (KI) therapy across 10 large US cancer centers was conducted. Investigators identified 123 patients who discontinued either ibrutinib or idelalisib (ibrutinib=93/idelalisb=30). Interestingly, 10% and 32% of ibrutinib (5% 140 mg, 5% 280 mg daily) and idelalisib patients (32% 100 mg BID), respectively, were initiated at doses less than FDA labeled dose. Further, 23% and 42% of ibrutinib (Ibr) patients and 30% and 65% idelalisib (Ide) patients had doses modified or held, respectively, prior to discontinuation. For patients who discontinued KI therapy, the median time on KI was 5 months. The most common reasons for KI discontinuation were toxicity (58% Ibr, 60% Ide), CLL progression (24% Ibr, 30% Ide), and RT DLBCL (8% Ibr, 7% Ide) (Mato et al, Abstract 80707, ASH 2015).

The "kinase inhibitor intolerant" patient population is therefore a unique CLL patient population in that they have at least SD to kinase inhibitor however, clinically cannot continue with therapy due to treatment related toxicity. This represents a population at risk for inferior outcomes and one that requires distinct study apart from patients who progress while receiving kinase inhibitor therapy. Additionally there have been no prospective studies reported to date that address the important question of sequencing kinase inhibitor therapies.

The purpose of this study is to evaluate the safety and efficacy of umbralisib in previously treated chronic lymphocytic leukemia (CLL) patients who are intolerant to prior BTK or PI3K-delta inhibitor therapy. This study will evaluate the progression-free survival of umbralisib in patients who are intolerant to prior KI therapy which is required to be a BTK (ie. ibrutinib) or PI3K-delta inhibitor (idelalisib, duvelisib, etc).

2 OBJECTIVES AND ENDPOINTS

2.1 STUDY OBJECTIVES

PRIMARY OBJECTIVE

 To determine the progression free survival of umbralisib in patients who were intolerant to prior BTK and/or PI3K-delta inhibitors.

KEY SECONDARY OBJECTIVES

- To evaluate the overall response rate (CR + PR) and duration of response of umbralisib in patients who were intolerant to prior BTK and/or PI3K-delta inhibitors.
- To evaluate Time to Treatment Failure with umbralisib as compared to the prior kinase inhibitor therapy in patients with CLL.
- To evaluate the safety profile of umbralisib as compared to the safety profile of the prior kinase inhibitor therapy in patients with CLL.

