Following Screening, qualified patients will be enrolled via an IWRS and receive the following: Umbralisib at 800 mg once daily During the study period, all patients will be evaluated for response by CT and/or MRI during Cycles 3, 6, 9, 12 and then at least every 6 cycles for 24 cycles, then every 12 cycles thereafter. Patients will be treated until disease progression, unacceptable toxicity or the end of the study. Upon the end of the study, patients without disease progression may be transitioned to an open label compassionate use study. We will plan to enroll approximately 55 subjects, and assuming 10% attrition, we will have approximately 50 subjects remaining for analysis. Enrollment is expected to be completed in approximately 12 months with 24 months follow up. The sample provides 82% power to detect a 12- month median survival versus an 8 month median representing the null hypothesis, using a one-sided one-sample log-rank test with a 5% type 1 error. Statistics The number of treatment interruptions and dose reductions will also be evaluated between the prior therapy with a BTK or PI3K-delta inhibitor compared to umbralisib. Safety will be examined on an ongoing basis while the study is being conducted. Adverse events will be recorded as per CTCAE v4.0, and be compared for

umbralisib to the prior treatment if data available.

LIST OF ABBREVIATIONS AND DEFINITIONS OF TERMS

	Abbreviations and Definitions of Terms
AE	Adverse Event
ALC	Absolute lymphocyte count
ALT	Alanine aminotransferase
AST	Aspartate aminotransferase
AUC	Area Under the Curve
BM	Bone Marrow
BTK	Bruton's Tyrosine Kinase
Ca	Calcium
CBC	Complete Blood cell Count
Cl	Clearance
CLL	Chronic Lymphocytic Leukemia
cm	Centimeter
Cmax	Maximum Concentration
CR	Complete Response
eCRF	Electronic Case Report Form
CRO	Contract Research Organization
CT	Computed tomography
CTCAE	Common Terminology Criteria for Adverse Events
CVA	Cerebro-Vascular Accident
D, d	Day
DSMB	Data Safety Monitoring Board
DLT	Dose Limiting Toxicity
DOR	Duration of Response
DRG	Data Review Group
EC	Ethics Committee
ECG	Electrocardiogram
ECOG	Eastern Cooperative Oncology Group
FCR	Fludarabine, Cyclophosphamide, Rituximab
FISH	Fluorescence in-situ hybridization
GCP	Good Clinical Practice
IEC/IRB	Independent Ethics Committee (IEC) or Institutional Review Board (IRB)
Ig	Immunoglobulin
ICH	International Conference on Harmonisation
IRC	Independent Review Committee
ITT	Intent-to-treat

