3.1 INCLUSION CRITERIA

Patients must meet all of the following inclusion criteria to be eligible for participation in this study:

- 1. Confirmed diagnosis of CLL as per the iwCLL (Hallek 2008) criteria
- CLL warranting therapy as per investigator discretion.
- 3. Patients must be off prior BTK and/or PI3K-delta inhibitor for at least 14 days following discontinuation without documented disease progression. This is to ensure the reason for discontinuation was intolerance, not disease progression as listed below, # 4 7. Patients may sign consent during the washout period.
- 4. For ibrutinib/BTK patients who experience related hematologic and non-hematologic toxicities and discontinue therapy (see bullet 7). Non-hematologic toxicities are limited to: Atrial fibrillation, Hypertension, Bleeding, Arthralgia, Rash, Diarrhea, Infection, Pneumonitis.
- For idelalisib/duvelisib patients who experience related hematologic and non-hematologic toxicities and discontinue therapy (see bullet 7). Non-hematologic toxicities are limited to: Pneumonitis, Transaminitis, Rash, Colitis, and Infection.
- 6. Other grade ≥ 2 non-hematologic toxicities not listed in 4 or 5, despite dose interruption and/or reduction, and defined by the treating investigator as "intolerant", will be evaluated individually by the study chair as part of eligibility criteria as part of the screening process.
- Prior therapy with a BTK inhibitor (ibrutinib, ACP-196, other) or a PI3K-delta inhibitor (idelalisib, duvelisib, other) which was discontinued, due to intolerance, within 12 months of the time of treatment initiation with umbralisib (Cycle 1/Day 1).
 - a. Intolerance defined as unacceptable toxicity where in the opinion of the investigator, treatment should be discontinued in spite of optimal supportive care as a result of one of the following:
 - i. ≥ 2 Grade ≥ 2 non-hematological toxicities (see list above, #4-6) as a cause of discontinuation, and/or;
 - ii. ≥ 1 Grade ≥ 3 non-hematological toxicity (see list above, #4-6), and/or;
 - iii. ≥ 1 Grade 3 neutropenia with infection or fever, and/or;
 - iv. Grade 4 hematological toxicities, AND the toxicities persistent to the point that the investigator chose to discontinue therapy due to toxicity / not progression.
 - v. Toxicity must resolve to ≤ grade 1 prior to umbralisib dosing.
- 8. Adequate organ system function, defined as follows:

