3.2 EXCLUSION CRITERIA

Patients who meet any of the following exclusion criteria are not to be enrolled to this study:

[figure not shown]
- 1. Patients receiving a BTK or PI3K-delta inhibitor within 14 days of Cycle 1/Day 1.
 - a. Corticosteroid therapy started at least 7 days prior to study entry (prednisone ≤10 mg daily or equivalent) is allowed as clinically warranted. Topical or inhaled corticosteroids are permitted.
- 2. Disease progression as defined by IWCLL (Hallek 2008) criteria as the indication for discontinuation on or within 14 days with a prior BTK or PI3K-delta inhibitor.
- 3. Prior treatment with umbralisib.
- 4. Prior autologous stem cell transplant within 3 months. Prior allogeneic hematologic stem cell transplant within 1 year and excluded if there is active graft versus host disease.
- 5. Anaphylaxis to prior kinase inhibitor therapy.
- 6. Evidence of chronic active Hepatitis B (HBV, not including patients with prior hepatitis B vaccination; or positive serum Hepatitis B antibody) or chronic active Hepatitis C infection (HCV), cytomegalovirus (CMV), or known history of HIV. If HBc antibody, HCV antibody or CMV is positive the subject must be evaluated for the presence of HBV, HCV, or CMV by DNA (PCR) See Appendix D.
- Known histological transformation from CLL to an aggressive lymphoma (i.e. Richter's transformation / Hodgkin Lymphoma).
- Evidence of ongoing systemic bacterial, fungal or viral infection, except localized fungal infection of skin/nails.
- Any severe and/or uncontrolled medical conditions or other conditions that could affect their participation in the study such as:
 - Symptomatic, or history of documented congestive heart failure (NY Heart Association functional classification III-IV) – See Appendix C
 - b. Myocardial infarction within 6 months of enrollment
 - c. QTcF >470 msec
 - d. Angina not well-controlled by medication
 - Poorly controlled or clinically significant atherosclerotic vascular disease including cerebrovascular accident (CVA), transient ischemic attack (TIA), angioplasty, cardiac/vascular stenting within 6 months of enrollment.

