10.4.1 RECORDING OF ADVERSE EVENTS

All adverse events of any subject during the course of the study will be reported on the case report form, and the investigator will give his or her opinion as to the relationship of the adverse event to

TGR-1202-201-CLL

study drug treatment (i.e., whether the event is related or unrelated to study drug administration – umbralisib). If the adverse event is serious, it should be reported as soon as possible and no greater than 24 hours to the sponsor or designee. Other untoward events occurring in the framework of a clinical study are also to be recorded as AEs (i.e., AEs that occur prior to assignment of study treatment that are related to a protocol-mandated intervention, including invasive procedures such as biopsies, medication washout, or no treatment run-in).

All AEs regardless of seriousness or relationship to umbralisib treatment spanning from Cycle 1/Day 1 until 30 calendar days (+/-7 days) after discontinuation or completion of either protocol-specific treatment as defined by the protocol for that subject, are to be recorded on the eCRF.

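### Two key secondary objectives compare umbralisib with the prior kinase inhibitor, but eligibility fixes toxicity discontinuation, qualifying toxicity and a TTF event at 100% on that drug

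*Combined protocol and SAP*

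**What the plan says.** Two of the three key secondary objectives in Section 2.1, repeated in the synopsis, are comparative. One is "To evaluate Time to Treatment Failure with umbralisib as compared to the prior kinase inhibitor therapy in patients with CLL". The other is "To evaluate the safety profile of umbralisib as compared to the safety profile of the prior kinase inhibitor therapy".

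The Statistics part of the synopsis says that "treatment interruptions and dose reductions will also be evaluated between the prior therapy" and umbralisib. It adds that adverse events will be compared for "umbralisib to the prior treatment if data available".

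Eligibility defines the prior course. Inclusion criterion 7 (Section 3.1) requires a BTK or PI3K-delta inhibitor "which was discontinued, due to intolerance, within 12 months of the time of treatment initiation with umbralisib". Items 7a(i) to (iv) define intolerance by graded toxicities, and item 7a(v) adds "Toxicity must resolve to ≤ grade 1 prior to umbralisib dosing". Inclusion criterion 3 requires at least 14 days off the drug without documented progression. Exclusion criterion 2 (Section 3.2) removes "Disease progression as defined by IWCLL (Hallek 2008) criteria as the indication for discontinuation on or within 14 days".

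Sections 2.2 and 9.9.2.2 define TTF from umbralisib Cycle 1/Day 1 to stopping treatment for any reason, and Section 9.9.2.2 plans only a Kaplan-Meier median. Sections 10.1 and 10.3 tabulate umbralisib adverse events, reasons for stopping treatment, and events that led to stopping.

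**The concern.** The comparator is the drug whose failure through toxicity made the subject eligible. Its results on the items that define eligibility are known before the first subject enrols, and they say nothing about how tolerable that drug is in general. A clinical study report that follows the objectives could set umbralisib beside a prior drug on which every subject had a qualifying toxicity and every subject stopped. Readers could take the difference as evidence of better tolerability, when the entry criteria fix one side of it.

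The TTF objective has a further gap. The only TTF definition starts at Cycle 1/Day 1 of umbralisib, so the start date for the prior drug is unstated. The objectives allow prior BTK and/or PI3K-delta inhibitors, and nothing says which is the comparator for a subject who took both.

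At stake is what two key secondary objectives can support. The primary PFS result does not use prior-drug data.

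**Working it through.** **1. The plan's own figures.** The synopsis plans 55 subjects and 10% attrition: 55 × 0.9 = 49.5, about 50. No design figure is given for the comparisons with prior therapy. The only design calculation is 82% power for PFS (median 12 against 8 months, one-sided 5%). I assumed exponential survival, uniform accrual over 12 months and a further 24 months of follow-up, with λ = ln 2 / 12.
- Event probability = 1 − (e^(−24λ) − e^(−36λ)) / (12λ) = 1 − (0.25 − 0.125) / 0.693 = 0.820.
- Expected events O = 50 × 0.820 = 41.0. Expected count at the null hazard E = 41.0 × 12/8 = 61.5.
- Power = Φ((61.5 − 41.0)/√61.5 − 1.645) = 83.4%.

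This is close to 82%, and the present point does not touch it.

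**2. What eligibility fixes on the qualifying prior drug.**

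| Item | Prior drug | Umbralisib | Source of the prior-drug value |
|---|---|---|---|
| Discontinued for toxicity | 100% | free | Inclusion 7 |
| At least one qualifying toxicity | 100% | free | Inclusion 7a(i) to (iv) |
| TTF event observed | 100% | free, may be censored | Inclusion 3 and 7: the drug has been stopped |
| Progression as the reason for stopping | 0% | free | Inclusion 3, exclusion 2 |

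The second row is a composite. It does not make any single named event, such as rash or colitis, 100%.

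**3. Consequence for the first two rows.** Let X = 1 if a subject had the item on the prior drug and Y = 1 if on umbralisib. Eligibility sets X = 1 for all n subjects. If k have Y = 1, then:
- difference in proportions (prior minus umbralisib) = n/n − k/n = (n − k)/n, which is never negative;
- subjects who favour umbralisib = n − k, and subjects who favour the prior drug = 0.

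With n = 50, the difference is (50 − k)/50. It is zero only at k = 50, when every subject also has the item on umbralisib. This holds for any true rates.

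**4. Items that eligibility does not fix.**
- *Interruptions and reductions.* Criterion 6 mentions them only for toxicities not listed in criteria 4 and 5. Section 1.3 reports, among patients who stopped a kinase inhibitor, doses modified in 23% (ibrutinib) and 30% (idelalisib) and held in 42% and 65%. These are well below 100%, so the argument in step 3 does not apply.
- *Other adverse events.* On umbralisib, Section 10.4.1 requires recording of "All AEs regardless of seriousness or relationship to umbralisib treatment spanning from Cycle 1/Day 1 until 30 calendar days" after treatment ends. For the prior drug, the documents mention medical history at screening (Sections 5 and 9.5) and the synopsis proviso about available data. Fuller capture on umbralisib works against it, while selection for intolerance works against the prior drug. The net direction is undetermined.
- *TTF.* Requiring the prior course to have ended excludes subjects still doing well on that drug, which tends to shorten prior TTF. Umbralisib is a later line in subjects already shown to be intolerant, and progression and death count as failures only on umbralisib, which can act the other way. The documents give no basis for netting these effects.

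**5. Prior-drug TTF.** The event, stopping for any reason, carries over. The start date does not, because Cycle 1/Day 1 belongs to umbralisib. Criterion 7 identifies the index drug when only one inhibitor qualifies, but not when two do.

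**6. Precision of the proposed addition.** For illustration, take 5 recurrences in 50 subjects: 5/50 = 10%. The exact (Clopper-Pearson) 95% limits are the 2.5th percentile of Beta(5, 46) and the 97.5th percentile of Beta(6, 45), which are 3.3% and 21.8%.

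**The case against.** The strongest reply is that the study enrols intolerant patients on purpose, and the Study Rationale and Section 1.3 say so openly. No test, pairing or success criterion is attached. The synopsis proviso about available data suggests a descriptive look, and Sections 9.9.2.2 and 10.3 analyse umbralisib alone. All of this is true. It justifies the population, but not a comparison with the drug that selected it. No section calls the comparison descriptive or states the limit.

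Other parts of the reply narrow the point, and I accept them:
- The synopsis names interruptions, dose reductions and adverse events for comparison, not discontinuation. Whether discontinuation is set beside 100% depends on how the safety-profile objective is read. The qualifying toxicities are adverse events, so the stated comparison does cover them.
- A reader might set the figure of upwards of 12% in Section 1.1 against 100% and infer the size of the artefact. The documents do not support this. That figure concerns kinase-inhibitor patients generally, without denominator or follow-up, and these subjects are selected for intolerance. Only the 100% follows from the plan.
- A reader might infer that TTF is biased towards umbralisib, and use the 5-month median in Section 1.3 to size the bias. That series includes patients who stopped for progression or transformation. Any calculation would also need an assumed look-back period for prior treatment, which the documents do not give.
- The eCRF is not among the documents, so fields for the qualifying toxicity may well exist.

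**Conclusion.** The point holds, and the sponsor should act on it. On the qualifying prior drug, toxicity discontinuation, at least one qualifying toxicity, and a TTF event are each 100% by eligibility. A contrast on the first two can only tie or favour umbralisib. This rests on the entry criteria alone and needs no modelling assumption beyond the criteria being applied as written.

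For other adverse events, interruptions, dose reductions and TTF, the comparison is confounded by selection, line of therapy and unequal data capture, and neither its direction nor its size can be stated. Prior-drug TTF lacks a start date and, for subjects with two inhibitors, an index drug.

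The consequence is limited to what the two comparative objectives can support. There is no inflated error rate to claim, because no test is planned, and the PFS analysis stands.

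**What to change.** 1. Reword the two objectives in Section 2.1 and the synopsis, and the comparison sentences in the synopsis Statistics text, so that umbralisib TTF (Kaplan-Meier) and umbralisib safety are evaluated on their own. Sections 9.9.2.2 and 10.3 already analyse them this way.
2. If prior-drug data are shown, present them as a descriptive display labelled as selected by eligibility, with no inference between drugs. Define prior-drug TTF there as first to last dose of the inhibitor stopped under criterion 7, and state which drug is used when two qualify.
3. As a cheap descriptive addition, report in the safety population the proportion of subjects whose own qualifying toxicity recurs at grade 2 or higher on umbralisib, with an exact 95% CI. Criterion 7a(v) supplies the baseline. This addresses the rationale in Section 1.1 that toxicity profiles do not overlap, without a comparator fixed at 100%. It is not needed to cure the defect in the objectives.

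The cost is wording, one definition and one table. The sponsor gives up a comparative statement. Some prior-drug dates or grades may need completing from screening records.
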